9.2	SOURCE DOCUMENTS.....	20
9.3	CASE REPORT FORMS	20
9.4	RECORDS RETENTION	23
10	STUDY MONITORING, AUDITING, AND INSPECTING	23
10.1	STUDY MONITORING PLAN	23
10.2	AUDITING AND INSPECTING	23
11	ETHICAL CONSIDERATIONS	24
12	STUDY FINANCES	24
12.1	FUNDING SOURCE	24
12.2	CONFLICT OF INTEREST.....	24
12.3	SUBJECT STIPENDS OR PAYMENTS	24
13	PUBLICATION PLAN	24

LIST OF ABBREVIATIONS

AE	Adverse Event/Adverse Experience
CFR	Code of Federal Regulations
CRF	Case Report Form
DSMB	Data and Safety Monitoring Board
FDA	Food and Drug Administration
GCP	Good Clinical Practice
HIPAA	Health Insurance Portability and Accountability Act
IDE	Investigational Device Exemption
IRB	Institutional Review Board
PHI	Protected Health Information
PI	Principal Investigator
SAE	Serious Adverse Event/Serious Adverse Experience
SOP	Standard Operating Procedure
UADE	Unanticipated Adverse Device Effect

Study Summary

Title	Single-site, Pilot Study Evaluating SimPull as a Primary Means of Lateral Patient Transfer
Running Title	SimPull A Pilot Study
IRB Protocol Number	22-004929
Phase	Pilot
Methodology	Investigational Device
Overall Study Duration	Two months
Subject Participation Duration	Two minutes
Objectives	To utilize SimPull as an alternative to current lateral patient transfer methods through the evaluation of SimPull as a feasible means of lateral patient transfer.
Number of Subjects	100
Diagnosis and Main Inclusion Criteria	
 Patients requiring lateral transfer for an invasive cardiac procedure to and from gurney to exam table. Patients requiring lateral transfer for an invasive cardiac procedure to and from exam table to gurney. Patient does not have compound fractures or cervical fractures present. Patient does not have skin damage or open wounds to the dorsal cavity. Patient or legally authorized representative (LAR) must be able/present to sign consent.
Study Device	SimPull Lateral Transfer Device
Duration of Exposure	N/A
Reference therapy	Note if there is a standard reference therapy against which the study product is being compared, or if the reference is a placebo.
Statistical Methodology	A very brief description of the main elements of the statistical methodology to be used in the study. (As few lines as possible).

1 Introduction

This pilot study will assess the use of the SimPull as an alternative to current lateral patient transfer methods, evaluating if SimPull is feasible as a primary means of lateral patient transfer.

This document is a protocol for a human research study. This study will be carried out in accordance with the procedures described in this protocol, applicable United States government regulations and Mayo Clinic policies and procedures.

1.1 Background

Lateral patient transfer (lateral transfer) is the act of moving a patient from one horizontal surface to another. Lateral transfer is needed for many reasons, including but not limited to admitting patients from a gurney to hospital stretcher, within hospitals for changing units and when going for imaging, surgery, or testing. Lateral transfers are the most common type of patient transfer, Occupational Safety and Health Administration (OSHA) mandates no more than 35 lbs. be lifted by an individual clinician, yet the average patient weight is nearly 200 lbs., meaning an average patient requires six clinicians to be moved per OSHA mandate. Customer discovery sessions found in typical acute care settings it takes 4-minutes on average to recruit each staff member for lateral transfers creating a 22-minute average time when following this OSHA mandate. As 22-minutes is unreasonable to do a transfer, clinicians are currently forced to ignore mandates to stay on schedule, resulting in 12,000 injuries to U.S. clinicians annually. Typically, overexertion injuries to backs, necks, shoulders, wrists, or elbows are not easily remedied; many of these injuries cause lifelong issues. While there are products available to support lateral transfers, these products have the same problem; they require a separate product to be placed underneath the patient to facilitate the transfer. To get patients on these transferrable surfaces an entirely manual process referred to commonly as “log-rolling” must be performed. This manipulation is attributable to up to 50% of injuries related to lateral transfer. Even with these products available, nurses sustain more injuries than any other profession in any other industry and patient transfer, specifically lateral transfer is a major contributor. When nurses sustain these injuries, it makes them vulnerable to further injury, sometimes unable to participate in transfers post-injury. This creates additional burden and increased risk to uninjured staff as they are held accountable to do the same transfers without support from injured staff. Nurses are in high demand and short supply, as the population ages and patient weight increases, supporting a safe work environment for clinicians is critical.

1.2 Investigational Device

SimPull is an automated lateral transfer device that will be used in the catheterization laboratory (cath lab) and electrophysiology laboratory (EP lab) throughout the pilot study. SimPull can complete a lateral transfer in two minutes by one user with zero work force allowing for a removal of the risk of injury while also providing 20-minute reduction in time per transfer. The device is comprised of several important components. The clamp, a unique barbell design utilizes a slip knot to engage to common bed sheets which are readily available under patients. The clamp is attached to an easily cleaned Biothane strap, which feeds into the

motor. The motor generates a pull force allowing up to 500 lbs. of patient weight to be transferred. The motor is housed in a unit, protecting the user, and providing a user interface with clear operating directions. A handheld remote with safety switches is incorporated to ensure staff can guide the patient, the device transfers the patient bearing nearly 100% of the patient's weight. The device utilizes an adjustable feature that allows the height of the device to match the frame of most typical hospital surfaces. The SimPull bumper has two positions, regular, and extended. Once the bumper is in the preferred position, the bumper lock should be engaged and remain locked for the duration of the transfer. The device is the size of a large vacuum on casters that can swivel 360 degrees, making it easy for one person to use and move about floors.

1.3 Clinical Data to Date

There is no available clinical research data to date on the SimPull investigation device.

1.4 Study Rationale and Risk Analysis (Risks to Benefits Ratio)

1.4.1 Study Rationale

The SimPull is a standalone lateral patient transfer device that can be used in environments with limited ceiling access and confined spaces in the acute care setting. The current available products to support lateral transfers, all have the same problem; they require a separate product for the patient to be on top of during transfer. To get patients on these transferrable surfaces is an entirely manual process referred to commonly as “log-rolling” must be performed. This manipulation is attributable to up to 50% of injuries related to lateral transfer. Even with these products available, nurses sustain more injuries than any other profession in any other industry and patient transfer, specifically lateral transfer is a major contributor. When nurses sustain these injuries, it makes them vulnerable to further injury, sometimes unable to participate in transfers post-injury. This creates additional burden and increased risk to uninjured staff as they’re held accountable to do the same transfers without support from injured staff.

1.4.2 Anticipated Risks

SimPull is a standalone lateral patient transfer device, that is not yet approved for market, making it an investigational use device. SimPull is meant to be used in many environments, meaning that in interacting with products that are not specifically made to be compatible with SimPull could result in some risk. Specifically, SimPull attaches to sheets under patients, if the sheets are not positioned well, the patient could turn during transfer. SimPull engages to the surfaces that the patient is being transferred to and from, if any surface is not in the braked or locked position there may be risk to the transfer. These risks are mitigated through sensors that prevent transfer if positioning is jeopardized. The last risk is that the device pulls the patient across one surface to another, in doing so there is some friction, though it has been intentionally reduced as much as possible, this friction could result in risk to the patient.

1.4.3 Potential Benefits

SimPull is the only device that allows for lateral transfer without “log-rolling” of the patient. Meaning the patient will experience a much smoother and more comfortable transfer. In addition, patient dignity is preserved as lateral transfer is currently a common patient dissatisfaction, with patients stating current methods negatively impact patient dignity. Lastly, a more efficient transfer for all patients means less non-clinical activities for staff resulting in more time spent with patients.

1.5 Anticipated Duration of the Clinical Investigation

The overall duration of the study is estimated at two months to enroll 100 subjects. The subjects will be enrolled in the study only during their cardiac catheterization or electrophysiology procedural visit.

2 Study Objectives

The objectives of proposed study are to:

1. Validate SimPull is feasible as a primary means of lateral patient transfer.
2. Validate SimPull is a safer method of lateral patient transfer than current alternatives objectively through data collection.
3. Validate SimPull increases staff satisfaction of lateral patient transfer.
4. Validate SimPull is a more efficient method of lateral patient transfer than current alternatives objectively through data collection.
5. To identify further product opportunities utilizing the SimPull core technology.

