2.1 Primary Objective

The primary objective of this study is to validate the SimPull is a more efficient method of lateral patient transfer than current alternatives.

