6.1 Sample Size Determination

Power estimate for feasibility outcomes

A sample size of 50 per transfer type (current method vs. SimPull) is estimated to achieve greater than 99% power to reject the null hypothesis of no difference in time to transfer using a two-sided two-sample equal variance t-test, assuming a mean time for transfer of 7 minutes under the current method and 3 minutes using SimPull, a standard deviation in both groups of 3.5 minutes, and a significance level of 0.5. A sample size of 50 transfers per type is estimated to achieve greater than 99% power to reject the null hypothesis of no difference in number of staff using a two-sided two-sample equal variance t-test, assuming a mean of 5 staff involved in transfer under the current method and 2 staff using SimPull, a standard deviation in both groups of 0.5, and a significance level of 0.5.

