6.2 Statistical Methods

Descriptive Statistics

Patient and transfer characteristics will be descriptively summarized by transfer type. Staff questionnaires will be descriptively summarized. The difference between transfer methods in time for transfer and number of staff involved in transfer will be tested using two-sample t-tests. A possible secondary analysis would test differences using a regression model adjusting for differences in patient or transfer characteristics. The difference between transfer methods in proportion of transfers following the OSHA mandate of no more than 35 lbs. lifted per staff member will be tested using a Chi-square or Fisher's exact test. A possible secondary analysis would test differences using a regression model adjusting for differences in patient characteristics. The paired differences in mean staff satisfaction scores and self-rated risk of injury scores will be tested using paired tests.

Primary Hypothesis:

SimPull lateral transfer device is a more efficient and safe method of lateral patient transfer than current methods of lateral transfer.

By recording patient weight and the number of clinicians engaged during manual transfers we can calculate the force needed by each individual. Example: Patient weight: 265 lbs., five clinicians: 53 lbs. per clinician (51% higher than the 35 lb. OSHA mandate). This data collection allows risk assessment of clinician injury during transfer in each location by

establishing weight pulled by clinicians and the number of transfers per day. Using this we can also forecast force required and risk of injury over time. Time to complete in seconds will be recorded for each lateral transfer.

Secondary Hypothesis:

Use of the SimPull device for lateral transfers will increase staff satisfaction and be a preferred method of lateral patient transfer.

Data collected pre and post SimPull implementation

- Employee Satisfaction
- Employee Perception of Injury Risk

Staff/Clinician Participant Survey:

Part 1 of Survey – Pre-Training

1. What is your preferred method for performing lateral patient transfers?
 - a. Manual, Assisted, Ceiling Lift, or Air Mattress
2. Do you feel at risk of injury performing lateral patient transfers?
 - a. No Risk, Minimal Risk, Neutral, Some Risk, High Risk
3. How likely do you feel you are to be injured during lateral patient transfer?
 - a. Not at all likely, Not Likely, Neutral, Likely, Very Likely

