6.3 Subject Population(s) for Analysis

All-treated population that was transferred using the SimPull device in the cardiac catheterization and electrophysiology procedure area.

7 Safety and Adverse Events

All adverse events occurring during the study, including those not meeting the criteria of an Unanticipated Adverse Device Effect (UADE) will be recorded on the appropriate case report form. Records of these events will be maintained and reports submitted to the FDA and IRB according to the regulatory requirements. Expected clinical adverse events and nonsignificant (not serious) clinical adverse events will not be reported. Expected clinical adverse events and anticipated adverse device effects are those listed in Section 1.5.2.

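### Objective 2 and the primary hypothesis claim SimPull is safer, but safety is compared only through a load proxy and perceived risk; no planned analysis compares observed staff injury or patient adverse events

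*Combined protocol and SAP*

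**What the plan says.** Objective 2 in Section 2 is to "Validate SimPull is a safer method of lateral patient transfer than current alternatives objectively through data collection". The primary hypothesis in Section 6.2 is that "SimPull lateral transfer device is a more efficient and safe method of lateral patient transfer than current methods of lateral transfer". The formal primary objective in Section 2.1 is narrower and does not name safety: "The primary objective of this study is to validate the SimPull is a more efficient method of lateral patient transfer than current alternatives". Section 2.2 covers staff satisfaction only.

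Section 3.2 lists five endpoints: transfer time, number of staff, proportion of transfers within 35 lb per staff member (patient weight divided by number of staff), staff satisfaction, and self-rated risk of injury. Section 6.2 plans tests for these five and nothing else. The power statement in Section 6.1 is headed as covering feasibility outcomes and deals with time and number of staff.

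Section 7 has adverse events recorded in study subjects, whichever group they are in, but plans no comparison between methods. Section 6.3 gives the analysis population as "All-treated population that was transferred using the SimPull device in the cardiac catheterization and electrophysiology procedure area".

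**The concern.** A claim that one method is objectively safer needs a comparison of something that measures harm. Section 1.4.2 names harms to the patient (turning during transfer, movement of an unlocked surface, friction), and the background rests on injury to clinicians. Neither kind of harm is an endpoint or has a planned analysis. The two endpoints nearest to safety are a calculated load and an opinion.

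A conclusion on safety would therefore rest on staff perception, on a ratio that does not describe a SimPull transfer, or on seeing few or no events in a small sample. Section 1.3 states that there are no earlier clinical data on the device, so nothing outside the study could fill the gap.

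**Working it through.** **1. The plan's own figure.** Section 6.1 states: "A sample size of 50 per transfer type (current method vs. SimPull) is estimated to achieve greater than 99% power". For time, the inputs are "assuming a mean time for transfer of 7 minutes under the current method and 3 minutes using SimPull" and "a standard deviation in both groups of 3.5 minutes, and a significance level of 0.5". The standardised difference is 4 / (3.5 × √(2/50)) = 4 / 0.70 = 5.71. Power is 0.9999 at a two-sided level of 0.05 and above 0.9999 at the printed level of 0.5. For staff (5 versus 2, SD 0.5) it is 3 / (0.5 × 0.2) = 30, so power is essentially 1. The stated figure reproduces at either level, and the printed 0.5 is a separate matter. This power is for efficiency and says nothing about harm.

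**2. Endpoint 3 as a safety measure.** Section 1.1 gives an average patient weight of nearly 200 lb; Section 6.1 gives 5 and 2 staff.
- Current method: 200 / 5 = 40 lb per person.
- SimPull: 200 / 2 = 100 lb per person.
- The 35 lb limit is met up to 5 × 35 = 175 lb with five staff, and up to 2 × 35 = 70 lb with two.

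Sections 1.2 and 5.1 say the device carries almost the whole weight, so 100 lb is not what each person lifts. The formula does not measure load under SimPull, and on the planning figures it tends to count against it.

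**3. Endpoint 5.** It is a self-rating on a questionnaire. Objective 2 asks for objective validation.

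**4. What 50 per group can show about observed harm.** The documents give no harm rate per transfer, only a national annual count of injuries with no denominator. The rates below are assumptions, shown as a range.

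*No events with SimPull.* The exact two-sided 95% upper limit for 0/50 is 1 − 0.025^(1/50) = 7.1%.

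*Power of a two-sided Fisher's exact test at 0.05, 50 per group, by full enumeration:*

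| Current method | SimPull | Power |
|---|---|---|
| 5% | 1% | 2% |
| 10% | 2% | 19% |
| 20% | 5% | 51% |

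*Best case, in which SimPull removes all harm.* With 0/50 under SimPull, 5/50 under the current method gives p = 0.056 and 6/50 gives p = 0.027, so at least 6 events are needed. The probability of 6 or more in 50 is 0.781 at a true rate of 15% and 0.832 at 16%. So 80% power needs a current-method rate of about 15% to 16%.

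**5. Design.** Under Section 5.2 the first 50 patients have the current method and the next 50 have SimPull, without randomisation. Even a clear difference in events could reflect calendar time or case mix.

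**The case against.** The best defence is that the plan does define safety in its own way. The rationale is clinician injury throughout, and the text under the primary hypothesis says that load per clinician allows injury risk to be assessed. On that reading Endpoint 3 is the objective safety comparison and Endpoint 5 supports it. This stands in part: safety-related quantities are compared between methods, and it would be wrong to say that the plan compares nothing bearing on safety. It does not rescue the claim, because Endpoint 3 misdescribes the load under SimPull and neither endpoint counts a harm.

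Three stronger readings are tempting and are not supported.
- A reader might infer from Section 6.3 that no comparison between methods is possible. Sections 3.1, 5.2 and 6.2 all provide for 50 current-method patients, and Section 6.2 tests between methods. Taken literally, Section 6.3 would void Endpoints 1 to 3 as well. It is a conflict to be reconciled and does not show that safety in particular goes uncompared.
- A reader might infer that 50 per group could never support a safety claim. That depends on the harm rate, which the documents do not give. Section 7.1 defines adverse events broadly and regardless of cause, so a low rate is not established.
- A reader might infer that all the needed data are already recorded. This holds for patients: the sentence in Section 7 excluding expected and non-serious events concerns reporting, and Section 7.2 still requires recording. It does not hold for staff. Section 7.1 defines adverse events in subjects, and others are reached only through the rule for serious, unanticipated and related problems.

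It is also fair that this is a pilot whose formal primary and secondary objectives do not name safety. That limits the weight of the point, but the hypothesis labelled primary does include safety.

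**Conclusion.** The point holds as headed. Objective 2 and the primary hypothesis promise a conclusion that no planned analysis of observed harm can support. The two proxies do not fill the gap: one is opinion, and the other gives 40 versus 100 lb per person at the planning figures, which tends to score SimPull as worse. It follows that Endpoint 3 is unlikely to produce a false finding of greater safety; its fault is that it is not a valid measure.

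The sample-size part is conditional on assumed rates. Power is 2% to 51% over the three pairs examined, and 80% power needs a current-method harm rate of about 15% to 16% even if SimPull removes all harm. With no events in 50 SimPull transfers, rates up to 7.1% remain compatible with the data. The sequential, non-randomised groups weaken a causal claim at any rate. The efficiency analyses are unaffected. The sponsor should make the change, but the study does not stand or fall by it.

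**What to change.** 1. Reword Objective 2 and the primary hypothesis so that the study describes safety under each method and does not validate superiority. Sections 2.1 and 2.2 need no change.
2. Add to Section 6.2 a descriptive table, by transfer method, of the adverse events already recorded under Section 7. Show events judged related to the transfer separately, so that complications of the cardiac procedure do not obscure them. Give exact 95% confidence intervals and no superiority test.
3. Add one yes/no item on staff injury to the transfer form for both methods, and include it in the table.
4. Reconcile Section 6.3 with the between-method analyses in Section 6.2, so that the population includes both groups.

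The cost is some rewording, one table and one new form item; no extra patients or visits are needed. The sponsor gives up a claim that SimPull is safer.

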2.1 Primary Objective

The primary objective of this study is to validate the SimPull is a more efficient method of lateral patient transfer than current alternatives.

2.2 Secondary Objective

The secondary objective of this study is to validate the SimPull increases staff satisfaction of lateral patient transfer.

3 Study Design

3.1 General Design

The methods for this pilot study are fundamentally straightforward; preliminary data collection, pilot and data collection, review, and publish. Data of 50 patients using current methods of lateral transfer and 50 patients using the SimPull device for lateral transfer will be

collected. Employees in the cardiac catheterization and electrophysiology procedural areas have been offered the opportunity to complete IRB study member requirements. Employees in the cardiac catheterization and electrophysiology procedural areas will be completing a survey for the 100 lateral transfers. Employees in the cardiac catheterization and electrophysiology procedural areas that have direct patient care responsibilities, completed IRB requirements, have been added as study members on the IRB application, and received hands on education on proper use of the SimPull device, may perform lateral transfers using the SimPull device and complete study surveys. Employees in the cardiac catheterization and electrophysiology procedural areas that have not completed IRB requirements and have not been added as study members on the IRB application, will perform standard of care for lateral transfers and will not complete study surveys. All study members will receive instruction prior to the study on how to complete the survey. The Principal Investigator and Co-Principal Investigator do not have consenting privileges and will not participate in the recruitment or consenting process.

